**Statistical Analysis:**

Assuming a historical ORR of 15%, per the phase II efficacy trial, Simon's optimal two-stage design calls for a total of 34 patients. A preliminary efficacy assessment will be performed following enrollment of the first 20 patients. If  $\geq 3/20$  enrolled patients achieve a CR, this is sufficient to continue enrollment for the remainder of the study. If  $\geq 9/34$  patients respond, we will reject ( $p < 0.05$ ) the null hypothesis that the true response rate of the regimen is less than or equal to 15%. If the true response rate is 35% or greater, this study design has 80% probability of rejecting the null hypothesis. If the true response rate is low at 15%, the probability of early termination is 60% with an expected sample size of 19 patients.

Toxicity will be monitored in the expansion phase using a Bayesian approach. Toxicity monitoring will begin when the 6th patient is evaluable for toxicity. It is expected that the toxicity rate is maintained at approximately 20% (maximum probability of DLT of 0.2, prior distribution (1,1), cohort size 1, and posterior probability  $> 80\%$ ). Enrollment will be paused if toxicity exceeds this rate.

The maximum number of patients enrolled (n=51) reflects an anticipated drop out of 15% (n=5) and enrollment of 6-12 additional patients if dose level 0 is deemed toxic.

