### **9.3 Dose De-escalation Design**

Assuming a historical ORR of 15%, per the phase II efficacy trial, Simon's optimal two-stage design calls for a total of 34 patients. A preliminary efficacy assessment will be performed following enrollment of the first 20 patients. If  $\geq 3/20$  enrolled patients achieve a CR, this is sufficient to continue enrollment for the remainder of the study.

If  $>9/34$  patients respond, we will reject ( $p<0.05$ ) the null hypothesis that the true response rate of the regimen is less than or equal to 15%. If the true response rate is 35% or greater, this study design has 80% probability of rejecting the null hypothesis. If the true response rate is low at 15%, the probability of early termination is 60% with an expected sample size of 19 patients.

The maximum number of patients enrolled ( $n=51$ ) reflects an anticipated drop out of 15% ( $n=5$ ) and enrollment of 6-12 additional patients if dose level 0 is deemed toxic.

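### The quoted 60% early termination and expected sample size of 19 cannot come from a 20-patient first stage, and the final success cut-off is ≥9/34 in one place and >9/34 in another

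*Combined protocol and SAP*

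**What the plan says.** The design is described twice in nearly the same words: in the Protocol Synopsis under Statistical Analysis, and in Section 9.3 (Dose De-escalation Design).

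- Design and null rate: "Assuming a historical ORR of 15%, per the phase II efficacy trial, Simon's optimal two-stage design calls for a total of 34 patients".
- Interim: "A preliminary efficacy assessment will be performed following enrollment of the first 20 patients". At least 3 of these 20 must reach CR: "enrolled patients achieve a CR, this is sufficient to continue enrollment for the remainder of the study".
- Power: "If the true response rate is 35% or greater, this study design has 80% probability of rejecting the null hypothesis".
- Behaviour under the null: "If the true response rate is low at 15%, the probability of early termination is 60% with an expected sample size of 19 patients".
- Final rule in the synopsis, 9 or more of 34: "\geq 9/34$ patients respond, we will reject".
- Final rule in Section 9.3, more than 9 of 34, that is 10 or more: ">9/34$ patients respond, we will reject".

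Stray symbols in the last two quotes come from reading the PDF. Both places attach p<0.05 to their own cut-off. Neither says whether the test is one-sided, and neither mentions a first stage of 9 patients.

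**The concern.** Expected sample size under a two-stage design is the first-stage size plus a non-negative amount. With 20 patients always enrolled in stage 1, it cannot be 19. So the stated properties must describe some other design, and the error rates claimed for the written one are in doubt.

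Two things are at stake. The first is the decision on the primary objective: a result of exactly 9 of 34 is positive under the synopsis and negative under Section 9.3, and nothing says which governs, so the criterion could be chosen after the data are seen. The second is futility protection: anyone relying on the stated 60% would believe that an inactive regimen usually stops early.

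**Working it through.** **Inputs** (synopsis, Statistical Analysis, and Section 9.3): null rate p0 = 0.15; target rate p1 = 0.35; N = 34; first stage n1 = 20; continue if ≥3, so stop if ≤2; final cut-off r = 9 (synopsis) or r = 10 (Section 9.3); claimed level 0.05, power 80%, early termination 60%, expected size 19. Assumptions: one-sided exact test (the usual Simon convention), a binding interim stop, and the same response endpoint at both stages.

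**Formulas**

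- Early termination: PET = P(X1 ≤ r1), with X1 ~ Bin(n1, p0).
- Expected size: E(N) = n1 + (1 − PET)(N − n1).
- Rejection probability at rate p: the sum, over x from r1 + 1 to n1, of P(X1 = x) × P(X2 ≥ r − x), with X2 ~ Bin(N − n1, p). At p0 this is alpha; at p1 it is power.

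**Step 1. Reproduce the plan's figures.** A search over two-stage designs with p0 = 0.15, p1 = 0.35, alpha ≤ 0.05 and power ≥ 0.80 returns as Simon's optimal design: n1 = 9, stop if ≤1, N = 34, reject if ≥9.

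- PET = 0.2316 + 0.3679 = 0.5995.
- E(N) = 9 + 0.4005 × 25 = 19.01.
- Alpha = 0.0474; power = 0.8107.

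This matches the label, the total, the 80% power, the 60%, the 19 and the synopsis cut-off. Among all first stages with N = 34, only n1 = 9 with stop at ≤1 gives both 60% and 19.

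**Step 2. The design as written (n1 = 20, stop if ≤2).**

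- PET = 0.0388 + 0.1368 + 0.2293 = 0.4049.
- E(N) = 20 + 0.5951 × 14 = 28.33.

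Reading the interim rule as stop at ≤3 does not rescue the figures: PET is 0.6477 and E(N) 24.93.

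**Step 3. The two cut-offs under each first stage.**

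| First stage | Success if | Alpha | Power |
|---|---|---|---|
| 20, stop ≤2 | ≥9/34 | 0.0581 | 0.8894 |
| 20, stop ≤2 | ≥10/34 | 0.0239 | 0.8037 |
| 9, stop ≤1 | ≥9/34 | 0.0474 | 0.8107 |
| 9, stop ≤1 | ≥10/34 | 0.0206 | 0.7433 |

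Ignoring the interim, P(X ≥ 9 | 34, 0.15) = 0.0587. The exact one-sided 95% lower bound at 9/34 is 14.6%, which does not exclude 15%.

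**Step 4. How often the two cut-offs disagree.** With the 20-patient stage, this is the difference between the two rejection probabilities:

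- true rate 15%: 0.0581 − 0.0239 = 0.034;
- true rate 25%: 0.4838 − 0.3353 = 0.149;
- true rate 35%: 0.8894 − 0.8037 = 0.086.

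**The case against.** - **The cut-off of 9 is not wrong in itself.** It is the correct one for the 9-patient first stage, with alpha 0.047. It exceeds 5% only when paired with the 20-patient stage. This stands, and it means the first stage and the cut-off have to be settled together.
- **The excess is small, and sidedness is not stated.** The excess is 5.8% against 5%. A two-sided 5% test would be stricter, so it would not rescue 9/34. Early termination, expected size and the conflict between cut-offs do not depend on sidedness.
- **The difference in sign could be a PDF-reading fault.** A lost underline would turn one sign into the other. However, the ≥ sign survives in the interim rule of the same Section 9.3, and >9 with a 20-patient stage does deliver the stated 80% power and p<0.05. The impossible expected size stands either way.
- **The endpoint wording differs between stages.** The interim counts CR, the final rule counts responders, and the primary objective is composite CR/CRh/CRi. If the interim counts strict CR only, early termination at a 15% composite rate is higher than 40.5%; for example, it is about 59% if the strict CR rate is assumed to be 11.5%. So 40.5% and 28.3 rest on a common endpoint. Expected size still cannot fall below 20.
- **The cut-off conflict matters only at exactly 9 of 34.** True, but the chance of landing there is about 15% at a true rate of 25%.

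**Conclusion.** The concern holds. The properties of Simon's optimal 9-patient-first-stage design have been attached to a design with a 20-patient first stage. As written, at a true rate of 15%, early termination is 40.5% rather than 60% and expected size is 28.3 rather than 19. An inactive regimen therefore continues about 60% of the time rather than 40%, and about 9 more patients are treated on average (28.3 − 19 = 9.3). The primary success rule contradicts itself. Under the synopsis version with the 20-patient stage, the claim of p<0.05 is false at 9/34.

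That an expected size of 19 is impossible, and that the two cut-offs conflict, needs no assumption beyond the text. The exact error rates rest on a one-sided exact test with a binding interim stop and one endpoint at both stages. This must be corrected before the final analysis, because it is the decision rule for the primary objective.

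**What to change.** State one matched pair of first stage and cut-off, identically in the synopsis and in Section 9.3. The documents do not show which was intended, so the sponsor must choose.

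1. **Keep the look at 20** (continue if ≥3). Success is more than 9 of 34, that is 10 or more. Restate alpha 0.024, power 0.80, early termination 40% and expected size 28, and drop the word optimal. This leaves the interim as written in both places.
2. **Keep the stated 60% and 19.** Change the first stage to 9 patients (continue if ≥2), with success at 9 or more of 34 (alpha 0.047, power 0.81). This changes when the interim takes place.

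Changing the cut-off alone can fail: 9 patients with >9 drops power to 74.3%, and 20 patients with ≥9 exceeds 5%. Whichever is chosen, state that the test is one-sided and name the same response endpoint for the interim and final counts, so that the quoted figures apply.

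The cost is protocol wording, with no increase in the 34 patients. Under the first option, the stated early-termination probability and expected size become less favourable.

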**Table 1: Schedule of Activities and Assessments – Screening & Cycle 1**

Protocol Activities 1 Cycle = 4 weeks (28 days)	Screening (Day-14 to -1)	CYCLE 1				
		Day 1-3	Day 5	Day 8	Day 15	Day 22
		Clinical Assessments				
Consent, Baseline Characteristics & Eligibility 	X					
Physical Exam	X	X 		X	X	X
ECOG Performance Status	X	X 				
Height	X					
Weight	X	X 		X	X	X
Vital Signs (BP, HR & Temp) 	X	X	X	X	X	X
Review of Con Meds & Adverse Events 	X	X	X	X	X	X
DLT/RP2D Safety Evaluation 		X	X	X	X	X
		Laboratory and Other Assessments				
CBC with Differential 	X	X	X	X	X	X
Serum Chemistry 	X	X	X	X	X	X
Mg, Phos, LDH, Uric Acid	X	X	X	X		
Coagulation Testing (PT/INR, PTT)	X					
Electrocardiogram 	X					
Pregnancy Test 	X	X 				
		Biospecimen Collections				
Bone marrow aspiration and biopsy 	X					X 
Pharmacodynamic Blood (PD) 	X					X
Next Generation Sequencing 	X					X
		Treatment				
Anti-TLS hydration/prophylaxis 	X	X				
Decitabine/cedazuridine (oral) 		X	X			
Venetoclax oral administration (daily) 		Ramp	Continuous once daily oral dosing 			

**Table 2: C1D22 Marrow involved:**

Protocol Activities 1 Cycle = 4 weeks (28 days)	PRE-REMISSION THERAPY				POST-REMISSION THERAPY 				POST-TREATMENT		
	CYCLE 2				CYCLE 1		CYCLE 2		CYCLE 3+	EOT (≤10d after last study dose) 	Follow-Up (28d + 7d after last study dose) 
	Day 1	Day 8	Day 15	Day 22	Day 1, 5	Day 15	Day 1	Day 15	Day 1		
Clinical Assessments											
Physical Exam	X		X		d1		X		X	X	X
ECOG Performance Status	X				d1		X		X	X	X
Height											
Weight	X				d1		X		X	X	X
Vital Signs 	X	X	X	X	X	X	X	X	X	X	X
Review of Con Meds & Adverse Events 	X	X	X	X	X	X	X	X	X	X	X
DLT/RP2D Safety Evaluation 	X										
Survival Follow-Up											X 
Laboratory and Other Assessments											
CBC with Differential 	X	X	X	X	X	X	X	X	X	X	X
Serum Chemistry 	X	X	X	X	X	X	X	X	X	X	X
Mg, Phos, LDH, Uric Acid											X
Coagulation Testing (PT/INR, PTT)											X
Electrocardiogram 											X
Pregnancy Test 											X
Biospecimen Collections											
Bone marrow aspiration and biopsy 				X 					C3d1	EOT / PD 	
Pharmacodynamic Blood (PD) 				X						EOT / PD 	
Next Generation Sequencing 				X					C3d1	EOT / PD 	
Treatment											
Decitabine/cedazuridine (RP2D) 					Per Protocol		Per Protocol		Per Protocol		
Venetoclax oral administration (daily) 					Per protocol						

**Table 3: C1D22 Marrow uninolved:**

Protocol Activities 1 Cycle = 4 weeks (28 days)	POST-REMISSION THERAPY 					POST-TREATMENT	
	CYCLE 1		CYCLE 2		CYCLE 3+	EOT (≤10d after last study dose) 	Follow-Up (28d + 7d after last study dose) 
	Day 1, 5	Day 15	Days 1, 5	Day 15	Day 1		
Clinical Assessments							
Physical Exam	d1		d1		X	X	X
ECOG Performance Status	d1		d1		X	X	X
Height							
Weight	d1		d1		X	X	X
Vital Signs 	X	X	X	X	X	X	X
Review of Con Meds & Adverse Events 	X	X	X	X	X	X	X
DLT/RP2D Safety Evaluation 	d1						
Survival Follow-Up							X 
Laboratory and Other Assessments							
CBC with Differential 	X	X	X	X	X	X	X
Serum Chemistry 	X	X	X	X	X	X	X
Mg, Phos, LDH, Uric Acid						X	
Coagulation Testing (PT/INR, PTT)						X	
Electrocardiogram 						X	
Pregnancy Test 						X	
Biospecimen Collections							
Bone marrow aspiration and biopsy 					C3d1	EOT / PD 	
Pharmacodynamic Blood (PD) 						EOT / PD 	
Next Generation Sequencing 					C3d1	EOT / PD 	
Treatment							
Decitabine/cedazuridine (RP2D) 	Per Protocol		Per Protocol		Per Protocol		
Venetoclax oral administration (daily) 	Per protocol						

**Notes:**

[figure not shown]
1. Informed consent must be obtained before any screening assessments are performed. Screening assessments are to be performed within 14 days prior to Day 1 of Cycle 1 unless otherwise noted. Assessments performed as standard of care within the screening window may be used for screening. Baseline characteristics include but are not limited to demographics, medical and surgical history, extent of disease, prior anti-cancer treatment.
2. Vital Signs to include: Blood pressure (BP), heart rate (HR) and temperature. To be done at least once on days indicated and thereafter, ideally prior to any receipt of study drug. Any additional recordings per local site's standard of care/ treating physician discretion.
3. Review and capture of all concomitant medications will be performed as indicated. Concomitant medications include prescription medications and over-the-counter preparations used by a patient within at least 14 days prior to first dose of protocol-defined treatment and continuing through at least the 28-day Follow-Up study visit. After signing informed consent, adverse events will be collected and followed at least until 28 days after a patient's final protocol-directed treatment with DEC-C/venetoclax (whichever occurs last) or until initiation of another anti-cancer therapy – whichever occurs first.
4. Surveillance for toxicity related to DEC-C/venetoclax to establish RP2D. For patients enrolled in the dose exploration (or dose de-escalation) part of the study, dedicated surveillance including satisfactory assessment of the physical exam and safety labs is required to help detect evidence of past or present DLT as having occurred during the first 28 days of protocol-indicated treatment. Expedited reporting of Dose Limiting Toxicity (DLT) required as outlined in [Section 5.2.4](#). See [Section 5.2.4](#) for definition of DLT and toxicities which, if experienced during the first 28 days after initiating protocol-indicated treatment, shall be considered dose limiting.
5. Hematology includes white blood cell count with differential, hemoglobin, hematocrit, and platelet count. Blood Chemistry to include sodium, potassium, chloride, bicarbonate or carbon dioxide, blood urea nitrogen (BUN), creatinine, glucose, total bilirubin, AST, ALT, alkaline phosphatase, calcium, albumin, and total protein.
6. One standard 12-lead electrocardiogram (ECG) using local site equipment during screening and EOT visits. Additional ECGs as clinically indicated.
7. For women of childbearing potential: Serum pregnancy test required during screening and either serum or urine pregnancy test required  $\leq 3$  days prior to first dose of protocol-indicated treatment and at End-of-Treatment. A woman of childbearing potential is defined as any female who has experienced menarche who has not undergone surgical sterilization (e.g. bilateral tubal ligation, total hysterectomy, or bilateral oophorectomy) at least 4 weeks prior to first dose of protocol-indicated treatment, or who is not postmenopausal. Menopause is defined clinically as 12 months of amenorrhea in a woman over 45 in the absence of other biological or physiological causes.
8. Patients must have at least 2-3 mL of bone marrow aspirate material obtained within 14 days of beginning treatment on this study. Post-enrollment tissue to be collected on Cycle 1 Day 22, Cycle 2 Day 22 (only if C1 Day 22 marrow is

involved), post-remission Cycle 3 Day 1 (acceptable windows up to 3 days before or after); and at End-of-Treatment ( $\leq 14$  days after treatment was discontinued) or at time of suspected progressive disease.

[figure not shown]
9. On a day of a bone marrow biopsy, matching peripheral blood pharmacodynamic (PD) blood samples are to be drawn PRIOR to procedure for correlative research. At any time during the study, if additional biopsy is performed as standard-of-care, then a sample of the tissue, if available, may be requested for research purposes. Pharmacodynamic studies will be drawn to assess the impact of DEC-C/venetoclax on immune function/recovery during treatment and correlated with clinical/study outcomes.
10. All patients will have next generation sequencing (NGS) performed on their relapsed marrow and all subsequent marrows performed while on study. If the standard of care NGS report is available prior to enrollment, this should not be repeated. If NGS testing is not indicated per the institutional standard of care, additional bone marrow aspirate may be sent to VUMC and NGS will be performed as a research test.
11. During the first three days of therapy, tumor lysis syndrome (TLS) precautions will include scheduled outpatient visits with TLS laboratory studies. Therapy with a uric acid reducing agent (e.g., allopurinol initiated at least 2-3 days prior to the start of therapy) is required. Laboratory monitoring for TLS (per institution standard of care) will occur prior to the first dose on cycle 1 day 1 and continue for the first three days of cycle 1. Unless contraindicated, allopurinol must be continued through the end of cycle 1. Intravenous fluids should be administered daily during the ramp-up period. Patients with clinical evidence of TLS should be hospitalized.
12. The study will provide decitabine/cedazuridine (DEC-C) to the sites. Treatment with DEC-C will begin on Cycle 1 Day 1 after receiving anti-TLS hydration/prophylaxis. It is intended that patients will receive DEC-C until progression of disease, unacceptable toxicity, revocation of consent, or for up to 12 months of post-remission therapy. DEC-C is to be taken without food at the same time each day. See [Section 5.2.1.2](#).
13. Sites will obtain commercial (standard of care) venetoclax. Venetoclax will begin on Cycle 1 Day 1 after receiving anti-TLS hydration/prophylaxis. Venetoclax dosing is ramped to 400mg/day. It is intended that patients will receive venetoclax until progression of disease, unacceptable toxicity, revocation of consent, or for up to 12 months of maintenance. Venetoclax is taken with food at the same time each day. See [Section 5.2.1.1](#).
14. On Cycle 1, Day 1 only: Physical exam; ECOG performance status; and weight will be obtained unless performed within the prior 7 days. Confirmation of a negative pregnancy test is required in all women of childbearing potential prior to beginning protocol-directed therapies.
15. All patients will undergo bone marrow aspiration and biopsy on cycle 1 day 22 to assess treatment response and for correlative studies. Patients with at least a partial response (PR) to treatment who receive a second cycle of full-intensity therapy will have repeat biopsy at cycle 2 day 22. Aspirate and matching PD blood samples will be sent for correlative studies.

16. Beginning in the post-remission phase: To accommodate scheduling, Day 1 and 15 visits/procedures may occur with flexibility of  $\pm$  3 days.
17. Reasonable effort should be made to complete End-of-Treatment (EOT) procedures on the day it is decided a patient will no longer receive protocol-indicated treatment. These procedures must be completed subsequent to and not later than 10 days after investigator decision to permanently discontinue protocol-indicated treatment with DEC-C or venetoclax (whichever treatment occurs last) and prior to any subsequent anti-cancer therapy.
18. At End-of-Treatment: If patient discontinues study treatment for reason other than progressive disease confirmed by biopsy procedure (e.g. due to adverse event), then every effort should be made to obtain fresh biopsy samples to evaluate response and to obtain biospecimens including matching PD blood samples for exploratory research. If progressive disease is suspected between scheduled study biopsies (e.g. due to peripheral blood counts), then fresh biopsy and PD blood samples must be collected in a subsequent procedure to evaluate for progressive disease and to obtain bio specimens for research purposes; if progressive disease is confirmed in that procedure and the patient will terminate the study as a result, then these procedures may be used as the end of treatment procedures.
19. Follow-up clinic visit to be completed within 28 to 35 days after patient's final protocol-indicated treatment with DEC-C or venetoclax (whichever occurs last). Documented attempt(s) must be made for patient return to the study clinic. It will not be considered a protocol deviation if the patient is physically unable to return for the follow-up visit; such circumstance should be recorded in the study documents, and as much of the follow-up information as possible should be obtained from local and outside facilities. Note: The study may continue to request results of laboratory data conducted outside of the study but related to peripheral blood counts or bone marrow biopsy, until progressive disease is ultimately confirmed.
20. Each patient will be followed for survival every 3 months ( $\pm$  14 days) after patient's final protocol treatment with DEC-C or venetoclax (whichever occurs last) until death, end of the study, until patient withdraws consent, or for a maximum of 2 years after the patient's final protocol-indicated treatment – whichever comes first. Survival contact can be made via clinic visit, chart review, obituary or similar observation (e.g. Social Security death index), or by telephone.

**Figure 1: Study Schema – Pre-Remission Phase.** All patients will initiate therapy as outlined below. Patients who achieve a leukemia free state on bone marrow biopsy may interrupt therapy and will proceed to the post-remission phase of the study.

**Figure 2: Study Schema – Initiation of post-remission therapy.** Post-remission treatment will begin after patients with marrow aplasia recover counts (defined as absolute neutrophil count  $\geq 1,000/\mu\text{l}$  and platelets  $\geq 50,000/\mu\text{l}$ ). In the setting of bone marrow aplasia and  $>$  Grade 2 neutropenia/thrombocytopenia, a BMBx will be performed every six weeks until count recovery or evidence of recurrent disease. If the day 22 bone marrow biopsy is cellular but negative for leukemia, and there is concern for persistent disease, post-remission therapy may begin without interruption.

 A 2nd Pre-remission cycle may be administered in patients with one prior cycle

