## **2 STUDY OBJECTIVES**

### **2.1 Primary Objectives:**

1. To assess the effect of DEC-C/venetoclax on the investigator-assessed composite CR rate (CR/CRh/CRi)

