### 7.4 Cycle 2 (Pre-remission Therapy; only if C1D22 marrow is involved)

#### 7.4.1 Cycle 2, Day 1

- Physical Exam
- ECOG performance status
- Weight.
- Vital Signs: Blood pressure (BP), heart rate (HR) and temperature.
- Concomitant medication and Adverse Event review.
- CBC with differential
- Blood chemistry

- Surveillance for and expedited reporting of Dose Limiting Toxicity (DLT) – see [Section 5.2.4](#) for DLT definition.
- Dose venetoclax/DEC-C as outlined in [Table 5](#) and [Table 6](#).

#### 7.4.2 Cycle 2, Day 8

- Vital Signs: Blood pressure (BP), heart rate (HR) and temperature.
- Concomitant medication and Adverse Event review.
- CBC with differential
- Blood chemistry
- Dose venetoclax as outlined in [Table 5](#) and [Table 6](#).

#### 7.4.3 Cycle 2, Day 15

- Physical Exam
- Vital Signs: Blood pressure (BP), heart rate (HR) and temperature.
- Concomitant medication and Adverse Event review.
- CBC with differential
- Blood chemistry
- Dose venetoclax as outlined in [Table 5](#) and [Table 6](#).

#### 7.4.4 Cycle 2, Day 22

- Physical Exam
- Vital Signs: Blood pressure (BP), heart rate (HR) and temperature.
- Concomitant medication and Adverse Event review.
- CBC with differential
- Blood chemistry
- Dose venetoclax as outlined in [Table 5](#) and [Table 6](#).
- Bone marrow aspiration/biopsy with additional aspirate sent for correlative science
- Next generation sequencing (Central/VUMC)
- PD studies (blood)

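### Note 15 ties the cycle 2 day 22 marrow to at least a PR, while Note 8, Table 2 and Section 7.4.4 tie it only to an involved cycle 1 day 22 marrow, so response may not be assessed alike in everyone who receives cycle 2

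*Combined protocol and SAP*

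**What the plan says.** The primary objective (Section 2.1) is the "investigator-assessed composite CR rate (CR/CRh/CRi"). Section 9.2 has response assessed by IWG criteria.

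The C2D22 marrow is governed in several places:

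- **Note 15**, attached to the C2D22 marrow cell of Table 2, first gives the cycle 1 day 22 (C1D22) marrow to all patients. It then continues: "Patients with at least a partial response (PR) to treatment who receive a second cycle of full-intensity therapy will have repeat biopsy" at C2D22.
- **Note 8**, attached to the label of the same row, lists "Cycle 2 Day 22 (only if C1 Day 22 marrow is" involved. It has no PR condition.
- **Table 2** is headed "C1D22 Marrow involved" and marks the C2D22 marrow for that whole population.
- **Section 7.4** is headed "Cycle 2 (Pre-remission Therapy; only if C1D22 marrow is involved"). Its day 22 list (Section 7.4.4) includes "Bone marrow aspiration/biopsy with additional aspirate sent for correlative science", again without a PR condition.

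On who may receive a second pre-remission cycle, the readable footnote under the study schema says only that such a "Pre-remission cycle may be administered in patients with one prior cycle". Figure 1 itself is not shown in the text available.

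Two other provisions bear on the point. Section 5.2.6.3 lets patients begin the post-remission phase once blasts have cleared from the marrow. Section 7.8.2 lists a marrow at end of treatment. For patients who stop for a reason other than biopsy-confirmed progression, Note 18 adds that "every effort should be made to obtain fresh biopsy samples to evaluate response".

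**The concern.** A composite CR cannot be credited without a marrow. In the readable text, C2D22 is the only scheduled marrow at the end of the second pre-remission cycle. The next one on the calendar, post-remission cycle 3 day 1, is reached only by patients already treated as being in remission.

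Note 15 moves from all patients at C1D22 to a response-qualified group at C2D22. A coordinator who looks up the footnote on that cell can fairly read the change as a restriction. A patient below PR after cycle 1 who clears blasts during cycle 2 might then not be examined when the response is present.

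Two things are at stake. First, whether a response is looked for could depend on earlier response and on which note a site follows, in a multicenter trial. Second, the error has one direction. The trial has a single arm tested against a fixed 15%, so a missed response lowers the observed rate and nothing in a control arm offsets it. The C2D22 sequencing and correlative blood samples are scheduled at the same visit and could be lost with the marrow.

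**Working it through.** **Step 1. The passages side by side.**

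| Place | Who has the C2D22 marrow | PR required? |
|---|---|---|
| Note 15 (on the Table 2 cell) | Patients with at least a PR who receive a second full-intensity cycle | Yes |
| Note 8 (on the row label) | Patients with an involved C1D22 marrow | No |
| Table 2 heading and cell | Patients with an involved C1D22 marrow | No |
| Sections 7.4 and 7.4.4 | Patients with an involved C1D22 marrow | No |

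**Step 2. Is there a patient on whom they differ?** Yes, on the readable text. Section 7.4 and the schema footnote admit a patient to cycle 2 without requiring a PR. Someone with an involved C1D22 marrow who is below PR can therefore receive cycle 2. Note 8, Table 2 and Section 7.4.4 give that patient the C2D22 marrow; Note 15 does not name that patient.

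**Step 3. What catches a response if the marrow is omitted?**

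- Entry to the post-remission phase requires marrow blast clearance (Section 5.2.6.3), so a patient who is to move on needs a marrow showing it.
- A patient who stops treatment should have an end-of-treatment marrow (Section 7.8.2 and Note 18). Its timing follows discontinuation rather than the end of cycle 2, and Note 18 asks for best effort. A short response could be gone by then.

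**Step 4. Scale.** The plan gives no figure for the share of responses first reached in cycle 2 by patients below PR at C1D22, so there is no plan figure to reproduce for the effect itself. Without any assumption about that share, one response missed among 34 patients lowers the observed rate by 1/34 = 2.9 percentage points.

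For illustration only, let *m* be the assumed fraction of true responses that go undetected, so that the observed rate is *p* = 0.35 × (1 − *m*). From the Synopsis and Section 9.3: first stage 20 patients, continue with at least 3 responses, total 34. The Synopsis rejects the null at 9 or more of 34 and Section 9.3 at more than 9, so both are shown. With rejection threshold *c*,

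Power = Σ (x = 3 to 20) P[Bin(20, p) = x] × P[Bin(14, p) ≥ c − x].

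The plan's 80% power is recovered first, at *m* = 0 with *c* = 10.

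| Assumed *m* | Observed rate | Power, more than 9/34 (c = 10) | Power, 9 or more/34 (c = 9) |
|---|---|---|---|
| 0 | 35.0% | 80.4% | 88.9% |
| 5% | 33.25% | 73.9% | 84.4% |
| 10% | 31.5% | 66.4% | 78.8% |
| 20% | 28.0% | 49.1% | 63.9% |

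The row *m* = 0 applies if sites follow Note 8 and Section 7.4.4. The other rows require that the marrow is omitted and that neither backstop recovers the response.

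**The case against.** The strongest reply is that Note 15 restricts nothing. It says that a certain group will have the biopsy; it does not use the word only, and it does not say that others go without. Where this protocol means to restrict the marrow it says so, as Note 8 does. Note 8 sits on the label of the very row in question, so the table points a reader to the wider rule as well as to Note 15. Section 5.2.6.3 also acts on the C2D22 marrow result without any PR condition. Note 15 may merely describe who was expected to go on to a second cycle, and Figure 1, which cannot be seen here, might confirm that.

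Much of this stands. A reader might infer that Note 15 bars the marrow below PR, or that such a patient has no scheduled marrow. The documents do not support either inference: Note 8, Table 2 and Section 7.4.4 schedule it, and the post-remission entry condition and the end-of-treatment marrow give further chances to see a response.

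The reply does not remove the conflict. Two footnotes on one table row state different conditions for the same procedure, and nothing says which prevails. If Figure 1 does confine cycle 2 to patients with at least a PR, the gap in assessed patients closes, but Note 8 and Section 7.4 would still state a different condition from Note 15.

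**Conclusion.** The point holds as an internal contradiction over who has the C2D22 marrow, with a plausible route to uneven ascertainment of the primary endpoint. It is not a settled rule that leaves patients below PR unassessed. Any bias would be downward.

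Its size cannot be derived from the documents. It ranges from zero upward, depending on how many patients below PR receive cycle 2, how many of them respond, how many sites read Note 15 as a restriction, and how often the backstops fail. A reader might take the power figures above as an expected loss. They are not: the 5% to 20% range is assumed, and every such response is taken as undetected. The conclusion also rests on the readable text about entry to cycle 2, since Figure 1 is not shown.

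It is worth correcting before the endpoint is analyzed, because the primary endpoint rests on this marrow and the correction is small.

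**What to change.** Reconcile Note 15 with Note 8, Table 2 and Section 7.4.4, so that response is assessed by the same C2D22 marrow in everyone who receives a second pre-remission cycle. For example, the second sentence of Note 15 could read: *Every patient who receives a second pre-remission cycle will have a repeat marrow at cycle 2 day 22, whatever the response at cycle 1 day 22.* This concerns assessment only and leaves open who receives a second cycle. If Figure 1 states a condition for that, Note 8, Section 7.4 and the schema footnote should be checked against it.

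The cost is a one-sentence amendment with the IRB approval at each center that Section 10.6.1 requires. It adds no procedure beyond those that Note 8, Table 2 and Section 7.4.4 already schedule. If patients have already been treated, the sponsor should also list those who received cycle 2 without a C2D22 marrow, so that the report can show how many were assessed for response only by a later marrow or not at all.
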